**8. STUDY POPULATION AND SAMPLE SIZE**

In an ideal scenario, the results of this study will point to a very low false positive rate when applying ADNEX and Modified Benign Simple Descriptors to masses in pregnancy. Ideally, all participating centres should have been 'tried and tested' by IOTA already to minimize issues with data collection and missing data.

Our sample population will come from Early Pregnancy Units and from Tertiary referral centres for ultrasound **with or without** an oncology department attached to it. The sample size estimation is based on data from Tertiary referral centres.

The table below gives the sensitivity, specificity, and false discovery rate (defined as 1 minus positive predictive value) based on ADNEX thresholds as estimated in surgically and conservatively managed masses in the IOTA 5 study (non-pregnant patients). It assumes a prevalence of malignancy in pregnant women presenting in tertiary referral centers of 8% (based on a survey of a number of IOTA recognized centers; unpublished data). At a risk threshold of 10% (risk of malignancy calculated by ADNEX), the false discovery rate may be too high (65%) because of the low prevalence of malignancy in pregnant women. A risk threshold of 25% to 40% (Dutch standard in non-pregnant women) appears to offer a good balance between sensitivity (detection of malignant masses) and false discovery rates (false positive results may lead to intervention during pregnancy in benign masses).

threshold	sensitivity	speci ficity	false discovery rate
(risk of malignancy according to ADNEX)	100*(number classified as cancer/number of cancer)		100*(number benign/number classified as cancer)
1	99.1	12.0	91.1
3	94.7	59.7	83.0
5	93.3	76.4	74.4
10	91.2	85.3	65.0
15	87.3	89.0	59.2
20	83.5	91.5	53.9
25	80.2	93.1	49.7
30	77.3	94.4	45.4
40	73.0	95.8	39.8
50	66.7	97.1	33.3

The table below assumed an average of 15 pregnant women per year per tertiary referral center and assumed a sensitivity of 73% and a specificity of 95.8%. With 19 centers included in the data collection, the expected total sample size in three years is 855 pregnant women and 68 malignancies. This allows us to estimate the specificity, sensitivity, and false discovery rate with a precision (width 95% CI/2) of 1%, 11% and 11%, respectively.

## International Ovarian Tumour Analysis (IOTA) in Pregnancy Study

Number of centers	n	n malignancy	True +ve	False -ve	True -ve	False +ve	Precision sensitivity	Precision false discovery rate	Precision specificity
20	900	72	53	19	793	35	11%	11%	1%
19	855	68.4	50	18	754	33	11%	11%	1%
18	810	64.8	47	17	714	31	11%	11%	2%
17	765	61.2	45	17	674	30	12%	12%	2%
16	720	57.6	42	16	635	28	12%	12%	2%
15	675	54	39	15	595	26	12%	12%	2%
14	630	50.4	37	14	555	24	13%	13%	2%
13	585	46.8	34	13	516	23	13%	13%	2%
12	540	43.2	32	12	476	21	14%	14%	2%
11	495	39.6	29	11	436	19	15%	14%	2%
10	450	36	26	10	397	17	15%	15%	2%
9	405	32.4	24	9	357	16	16%	16%	2%
8	360	28.8	21	8	317	14	17%	17%	2%
7	315	25.2	18	7	278	12	18%	18%	2%
6	270	21.6	16	6	238	10	20%	20%	3%
5	225	18	13	5	198	9	22%	21%	3%
4	180	14.4	11	4	159	7	24%	24%	3%
3	135	10.8	8	3	119	5	28%	27%	4%
2	90	7.2	5	2	79	3	33%	33%	5%
1	45	3.6	3	1	40	2	42%	42%	8%

The table below repeats the same calculation, now assuming sensitivity of 80.2% and specificity of 93.1%. Including 19 centers allows us to estimate the specificity, sensitivity, and false positive rate with a precision (width 95% CI/2) of 2%, 11% and 10%, respectively.

Centre Number	n	n malignancy	True +ve	False -ve	True -ve	False +ve	Precision sensitivity	Precision false discovery rate	Precision specificity
20	900	72	58	14	771	57	11%	10%	2%
19	855	68.4	55	14	732	54	11%	10%	2%
18	810	64.8	52	13	694	51	11%	10%	2%
17	765	61.2	49	12	655	49	12%	11%	2%
16	720	57.6	46	11	617	46	12%	11%	2%
15	675	54	43	11	578	43	12%	11%	2%
14	630	50.4	40	10	540	40	13%	12%	2%
13	585	46.8	38	9	501	37	13%	12%	2%
12	540	43.2	35	9	463	34	14%	13%	2%
11	495	39.6	32	8	424	31	15%	13%	2%
10	450	36	29	7	385	29	15%	14%	3%
9	405	32.4	26	6	347	26	16%	15%	3%
8	360	28.8	23	6	308	23	17%	15%	3%
7	315	25.2	20	5	270	20	18%	17%	3%

## International Ovarian Tumour Analysis (IOTA) in Pregnancy Study

6	270	21.6	17	4	231	17	20%	18%	3%
5	225	18	14	4	193	14	22%	20%	4%
4	180	14.4	12	3	154	11	24%	22%	4%
3	135	10.8	9	2	116	9	28%	25%	5%
2	90	7.2	6	1	77	6	33%	30%	6%
1	45	3.6	3	1	39	3	42%	39%	9%

In addition, below are the minimum required sample sizes to demonstrate that IOTA-ADNEX has clinical utility in pregnant women at a range of thresholds for the IOTA-ADNEX model.

Threshold	Assumed Standardized Net Benefit	Assumed sNB treat all	sNB treat none	Target precision sNB (width 95% CI/2)	N required (pregnant patients with eligible mass)
5%	0.790	0.395	0	0.395	28
25%	0.538	<0	0	0.518	57
40%	0.408	<0	0	0.388	165
50%	0.334	<0	0	0.314	325

With a sample size of 855 patients and assuming a C-statistic of 0.90, we can calculate the C-statistic with a precision (width of CI/2) of 0.04. With respect to calibration, with 855 patients we have enough data to detect if 54 cancers were predicted instead of 68 observed (O/E=1.26), and to detect if 86 cancers predicted instead of the 68 observed (O/E=0.80). We do note that the sample size is insufficient to detect an O/E of 1.10 or an O/E of 0.90. To detect miscalibration-in-the-large of this magnitude would require 4389 patients.

We conclude that with 855 patients, this study will be sufficiently powered to obtain an estimate of the primary outcome, the false discovery rate of ADNEX at a risk threshold of 40%, with a precision of 11%. The study is also sufficiently powered to study the following secondary outcomes with sufficient precision: diagnostic accuracy (sensitivity and specificity), the C-statistic, and clinical utility (quantified by the Net Benefit) of ADNEX. The study is powered to detect moderate to large differences between (average) predicted and (average) observed risks, but underpowered to detect minor miscalibration.

Moreover, we will validate the IOTA-ADNEX model at 10%, 25%, 40%, and 50% risk thresholds. Intervening when the risk of malignancy is 10% or higher is a very sensitive approach with few missed malignancies, but may lead to too many unnecessary interventions during pregnancy. In contrast, intervening when the risk of malignancy is 50% or higher will yield a much more specific approach, with fewer interventions during pregnancy, but may lead to more missed cancers

Finally, data from adnexal masses encountered in two early pregnancy units will be collected and analysed separately to examine the distribution of predicted risks of malignancy and referral rates to tertiary care if ADNEX were used for triage (referral based on clinical decision at early pregnancy unit). In a period of three years and with an expected 5000 deliveries per center per year, we expect 30,000 pregnant women. With an expected prevalence of adnexal masses of 6%, we expect data on 1800 masses and at a BOT rate of 3-5% when an adnexal mass is picked up in pregnancy, between 50-90 malignancies (i.e. BOTs and invasive).

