### ***7.2 Secondary Outcome Measures***

- Estimation of the false discovery rate when the 2-step strategy (i.e. Modified Benign Simple Descriptors followed by ADNEX) is applied at 11-14 weeks.
- Estimation of the false discovery rate when the ADNEX Model and the 2-step strategy (i.e. Modified Benign Simple Descriptors followed by ADNEX) are applied at any time point during pregnancy;
- Estimation of the ability of the ADNEX model and of the 2-step strategy (sensitivity, specificity, C-index, calibration intercept, calibration slope, clinical utility) to discriminate between benign and malignant adnexal masses at 11-14 weeks gestation.
- Estimation of the ability of the ADNEX model and the 2-step strategy (sensitivity, specificity, C-index, calibration intercept, calibration slope, clinical utility) to discriminate between benign and malignant adnexal masses when detected at any time point in pregnancy;
- Evaluation of change in morphology of ovarian masses throughout pregnancy based on subjective assessment;
- Evaluation of change throughout pregnancy and postpartum in number, size, colour score, and morphology of papillations based on subjective assessment.

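### Section 8 presents 95% confidence limits for O/E as detectable miscalibration (power about 50%), and its second precision table uses 73% instead of the stated 80.2% sensitivity in two columns

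*Protocol*

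**What the plan says.** Section 8 bases its figures on 855 women: "With 19 centers included in the data collection, the expected total sample size in three years is 855 pregnant women and 68 malignancies". The assumed prevalence of malignancy is 8%.

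For calibration, it states: "With respect to calibration, with 855 patients we have enough data to detect if 54 cancers were predicted instead of 68 observed (O/E=1.26". For the opposite direction it claims enough data "to detect if 86 cancers predicted instead of the 68 observed (O/E=0.80". It then says the sample is too small for an O/E of 1.10 or 0.90: "To detect miscalibration-in-the-large of this magnitude would require 4389 patients". The conclusion is: "The study is powered to detect moderate to large differences between (average) predicted and (average) observed risks". The same sentence calls the study underpowered for minor miscalibration. No power level, test or confidence interval is given for calibration.

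Section 7.2 lists calibration among the secondary outcomes ("sensitivity, specificity, C-index, calibration intercept, calibration slope, clinical utility"), and section 8.1 names it again.

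The first precision table assumes a sensitivity of 73% and a specificity of 95.8%. The second is introduced by: "The table below repeats the same calculation, now assuming sensitivity of 80.2% and specificity of 93.1" (per cent). At 19 centres it is said to "estimate the specificity, sensitivity, and false positive rate with a precision (width 95% CI/2) of 2%, 11% and 10" (per cent).

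**The concern.** To say that a study can detect a departure, and is powered to do so, is to say that it would probably find the departure if it were there. A figure obtained only by asking when a 95% interval stops covering 1 does not show that. A true value exactly at such a limit is found about half the time. Readers planning to interpret calibration would take O/E 1.26 or 0.80 as reliably detectable, and would take 4389 as a usable sample size for smaller departures.

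In the second precision table, the sensitivity-precision column is identical to that of the first table in all 20 rows, although the assumed sensitivity rises from 73% to 80.2% and the true-positive and false-negative counts change (50 and 18 become 55 and 14 at 19 centres). The precision of a proportion should improve as it moves away from one half.

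The sentence before that table also names the wrong quantity. The false discovery rate is the primary outcome measure, so its name should be exact.

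**Working it through.** **Inputs from section 8.** n = 855; prevalence 8%, so 855 × 0.08 = 68.4 expected malignancies; 95% two-sided intervals; sensitivity and specificity 73% and 95.8% (first table), 80.2% and 93.1% (second table).

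**1. The plan's calibration figures for 855 women**

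- SE of ln(O/E) = √[(1 − 0.08)/68.4] = √(0.92/68.4) = 0.1160.
- 95% factor = exp(1.96 × 0.1160) = 1.255; its reciprocal is 0.797.
- Predicted counts at the limits: 68.4/1.255 = 54.5 and 68.4 × 1.255 = 85.9.

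These are the plan's 54 and 86, and its O/E of 1.26 and 0.80. With exactly 68 observed, the interval is 1.002 to 1.58 for 54 predicted and 0.63 to 0.993 for 86 predicted. Both only just exclude 1.

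**2. Power at those values**

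Power = Φ(|ln O/E|/0.1160 − 1.96):

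| True O/E | Power with 855 |
|---|---|
| 68/54 = 1.26 | 51% |
| 68/86 = 0.79 | 53% |
| exactly 0.80 | 49% |

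An exact binomial calculation gives 54% for 54 predicted and 51% for 86 predicted.

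A test of the calibration intercept that conditions on each woman's predicted risk is more efficient. It needs a risk distribution that the protocol does not give. I assumed normally distributed logit risks with SD 2.17, centred to give 8% prevalence and C = 0.90, and predictions shifted by a constant. The SE of the intercept is then 0.150, and power is 65–66% for 54 predicted and 68–69% for 86 predicted (Wald and score tests). Only this one shape was tried.

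**3. The figure of 4389**

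- A 95% interval running from 0.90 to 1.10 has log half-width ln(1.10/0.90)/2 = 0.1003.
- With 0.92/0.08 = 11.5, N = 11.5 × (1.96/0.1003)² = 4388.4, which rounds up to 4389.
- At N = 4389 the SE is √(11.5/4389) = 0.0512, the interval around O/E = 1 is 0.905 to 1.106, and power is 46% at O/E 1.10 and 54% at 0.90.

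**4. What 80% power would mean** (a convention, not in the protocol; multiplier 1.96 + 0.84 = 2.80)

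- With 855 women, the test of O/E: exp(±2.80 × 0.1160) = 1.38 and 0.72, or about 49 and 95 predicted.
- With 855 women, the intercept test under the assumption in step 2: O/E about 1.32 and 0.77, or about 52 and 89 predicted.
- N for the test of O/E = 11.5 × (2.80/ln O/E)²: about 9,940 for 1.10 and about 8,130 for 0.90.

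**5. The precision tables**

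Exact (Clopper–Pearson) half-widths on unrounded expected counts reproduce all 60 precision cells of the first table and all 20 specificity cells of the second, which identifies the method. For the other two columns of the second table:

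| Sensitivity used | Sensitivity cells matched | False discovery rate cells matched |
|---|---|---|
| 80.2% (stated) | 0 of 20 | 8 of 20 |
| 73% (first table) | 20 of 20 | 20 of 20 |

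The counts themselves do use 80.2%: at 19 centres, 0.802 × 68.4 = 54.9 true positives and 13.5 false negatives. The 19-centre row of the second table:

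| Precision | Printed | At 73% | At 80.2% |
|---|---|---|---|
| Sensitivity | 11% | 11.06% | 10.03% |
| False discovery rate | 10% | 9.95% | 9.72% |
| Specificity | 2% | 1.84% | 1.84% |

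Across the table, sensitivity precision is printed 1 to 2 points too wide in 20 of 20 rows, and false discovery rate precision 1 point too wide in 12 of 20.

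**6. The label**

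The 10% belongs to the column headed false discovery rate, defined earlier in section 8 as 1 minus the positive predictive value. The false positive rate is 1 minus specificity and would have the specificity precision, 2%.

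**The case against.** The best defence is that section 8 is about precision throughout. Its half-widths are defined as such, it names no test and no power level, and it says the study is sufficiently powered for the primary outcome when it means an 11% half-width. Read literally, the calibration sentences are then true: with 68 observed and 54 or 86 predicted, the interval does exclude 1. The section also admits that the sample cannot settle small departures.

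Part of this stands. The values 1.26 and 0.80 are not miscalculated; the fault is in what they are said to show. But for the primary outcome the section states the precision beside the word powered. For calibration it states neither an interval nor a precision, and it contrasts being powered for larger differences with being underpowered for minor ones. Readers will take that as a power statement.

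A second objection is that 4389 does not follow the criterion behind 54 and 86. That is right: requiring the interval just to exclude 1 would give 11.5 × (1.96/ln O/E)² = 4,863 for O/E 1.10 and 3,980 for 0.90. The match to a 0.90–1.10 interval is inferred, though it reproduces the figure exactly after rounding up. Under either criterion 4389 has no power term.

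The 65–69% intercept-test power rests on an assumed risk distribution. The conclusion and the fix do not depend on it.

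The table error is conservative, concerns the 25% threshold and changes no design decision. The mislabelled rate is evident from the column heading below it. Both are still stated errors.

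**Conclusion.** The concern holds and is minor. The calibration figures are confidence-interval criteria presented as detectable effects. At the stated O/E values, 855 women give about 50% power on the test of O/E, or 65–69% on an intercept test under the assumed risk distribution. The claim for moderate to large differences is therefore not supported by the calculation behind it; the admission about minor miscalibration is sound. These results assume 8% prevalence, as the protocol does.

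In the second precision table, two columns contradict the stated sensitivity, and the sentence introducing it misnames the false discovery rate. The primary-outcome precision of 11% at the 40% threshold reproduces, and the recruitment target is unaffected.

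**What to change.** - **Calibration figures.** Describe them as interval criteria. For example: *Under good calibration, the expected 95% CI for O/E with 855 women is about 0.80 to 1.26. It just excludes 1 when 54 or 86 malignancies are predicted against 68 observed, which corresponds to about 50% power for a test of O/E. A CI from about 0.90 to 1.10 would need 4389 women.*
- **Wording.** Remove the language of detection from all three calibration statements. In the conclusion, replace the powered and underpowered contrast with a statement about precision.
- **If a detectable effect is wanted.** Name the test and the power, and apply the same standard to 855 and to the larger sample size.
- **Second table.** Recompute the sensitivity and false discovery rate precision columns at 80.2%. The introductory sentence should then name specificity, sensitivity and false discovery rate, with 2%, 10% and 10%.

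The cost is a correction to text and one table. The calibration claim becomes weaker and the second table slightly more favourable. Sample size, recruitment and the primary outcome do not change.

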### **PRIMARY OUTCOME MEASURE**

False discovery rate (number of benign masses / number of masses classified as malignant) when using the ADNEX Model to discriminate between benign and malignant adnexal masses at 11-14 gestational weeks in pregnancy.

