## **6. METHOD and DATA COLLECTION**

### ***6.1 General Process***

We plan an initial recruitment period of 36 months. Women will be recruited to p-IOTA if found to have an adnexal mass (either newly diagnosed or previously known) at an ultrasound examination performed **at any gestational age**.

Patients will be managed as per local clinical guidelines specific to the case, with all clinical decisions taken by lead clinicians according to current policy and practice. If a patient consents to taking part in the study, the number of scans will be determined by the p-IOTA protocol.

For patients managed surgically, no follow-up ultrasound examinations after surgery will be required. Follow-up for these women is arranged by their clinicians as per clinical practice.

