### ***6.2 Study flow***

**Figure 1-3** illustrate the study flow.

**First arm (*primary objective - figure 1*):** Adnexal mass scanned at 11-14 weeks. If the decision is to manage the adnexal mass conservatively, the patient is to be re-scanned once more: 0 - 90 days postpartum. In addition, the patient will be asked to enter into the third arm of the study (see below) knowing that she can opt out from that arm at any point. If she consents to participate in the third arm, she will participate in a series of longitudinal examinations as described for the third arm.

All patients with a mass detected before 11 weeks will also be scanned at 11-14 weeks and can enter all three arms of the study. In this scenario, if more than one scan is performed during pregnancy before 11 weeks, only the first of several scans before 11 weeks will be included for the second and third arms of the study (see below).

**Second arm (*secondary objective - figure 2*):** Adnexal mass is seen for the first time during that pregnancy at any gestation. If the decision is to manage the adnexal mass conservatively, the patient is to be re-scanned once more: 0 - 90 days postpartum. For patients with a mass detected before 11 weeks, see also above (they will be re-scanned at both 11-14 weeks and at 0-90 days postpartum).

In addition, the patient will be asked to enter into the third arm of the study (see below) knowing that she can opt out from that arm at any point. If she consents to this, she will participate in a series of longitudinal examinations as described for the third arm.

**Third arm (*secondary objective - figure 3*):** Patients from the first and second arms who agree to enrol into the third arm i.e. longitudinal examination of an adnexal mass during pregnancy. For the purposes of the longitudinal evaluation, the time points for the ultrasound examination are:

- initial presenting scan if <11 weeks;
- 11-14 weeks;
- 16 week scan - endometriomas ONLY;
- second trimester routine scan (18-22 weeks);
- 30-34 weeks;
- any additional scans during pregnancy which resulted in either conservative management with extra scans or surgical intervention (with reason for the extra scan or for surgery documented);
- 0-90 days postpartum.

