### ***6.5 Study Closure***

We aim to recruit approximately 855 pregnant patients from 19 tertiary referral centres, with a minimum study duration of three years (please refer to [section 7](#)).

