## **7. STUDY OUTCOME MEASURES**

### ***7.1 Primary Outcome Measures***

- Estimation of the false discovery rate when the ADNEX Model is applied at 11-14 weeks.

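### The 11% precision stated for the primary false discovery rate uses all 855 any-gestation recruits, although only women with an 11-14 week ADNEX result can enter that outcome

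*Protocol*

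**What the plan says.** **Primary outcome.** The Study Summary defines it as the FDR "when using the ADNEX Model to discriminate between benign and malignant adnexal masses at 11-14 gestational weeks in pregnancy". Section 7.1 repeats the restriction: "Estimation of the false discovery rate when the ADNEX Model is applied at 11-14 weeks".

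**Who is recruited.** Section 6.1 admits women whose mass is found at an "ultrasound examination performed at any gestational age". The second arm in section 6.2 is described in the same way: "Adnexal mass is seen for the first time during that pregnancy at any gestation". For early detections, section 6.2 adds: "All patients with a mass detected before 11 weeks will also be scanned at 11-14 weeks".

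**Where 855 comes from.** Section 8 assumes 15 pregnant women per tertiary centre per year, 19 centres and three years, with no limit on gestation, and concludes that "the expected total sample size in three years is 855 pregnant women and 68 malignancies". Section 6.5 uses the same number as the recruitment target: "We aim to recruit approximately 855 pregnant patients from 19 tertiary referral centres".

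**What is claimed for it.** Section 8 ends: "We conclude that with 855 patients, this study will be sufficiently powered to obtain an estimate of the primary outcome". It names that outcome as the FDR at the 40% threshold and gives a precision of 11%, where precision is half the width of the 95% confidence interval.

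**The concern.** One number serves two populations. In section 6.5 the 855 is everyone recruited, at whatever gestation. In the conclusion of section 8 it is the number of women contributing to an outcome measured in one gestational window. No step in section 8 leads from the first to the second, and section 8.1 itself lists the 11-14 week and any-time validations separately.

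The protocol foresees recruits who will have no 11-14 week ADNEX result:

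- Women first included after 14 weeks. Section 6.2 admits them to the second arm and makes explicit CA125 provision for an inclusion scan after 14 weeks.
- Women whose mass is found before 11 weeks and who go to surgery with no further scan. Section 6.2 keeps them in the study with histology as the outcome.
- Women whose mass is found before 11 weeks and has been replaced by a normal ovary by the next scan. Section 6.2 ends their follow-up there, with no mass left to classify.

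Other masses found before 11 weeks are re-scanned in the window and are not lost by design.

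At stake is the advertised precision of the headline estimate. FDR precision depends on the number of ADNEX-positive women, about 83 of the 855, so each positive woman who presents too late reduces it directly.

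**Working it through.** **Inputs (section 8).** 19 centres, 15 women per centre per year, 3 years; prevalence of malignancy 8%; sensitivity 73% and specificity 95.8% at the 40% threshold.

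**Step 1: reproduce the plan's figure.**

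- n = 19 × 15 × 3 = 855
- Malignant = 0.08 × 855 = 68.4; benign = 855 − 68.4 = 786.6
- True positives = 0.73 × 68.4 = 49.9
- False positives = (1 − 0.958) × 786.6 = 33.0
- ADNEX-positives = 49.9 + 33.0 = 83.0
- FDR = 33.0 / 83.0 = 39.8%

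The exact (Clopper-Pearson) limits for x false positives among c ADNEX-positives are the 2.5% quantile of Beta(x, c − x + 1) and the 97.5% quantile of Beta(x + 1, c − x). With x = 33.04 and c = 82.97 they are 29.2% and 51.2%. The half-width is 10.97%, which the plan states as 11%. This method reproduces the FDR and sensitivity columns in all 20 rows of the first precision table. In the 19-centre row the four cells add to the whole total: 50 + 18 + 754 + 33 = 855. Every recruit has therefore been given an ADNEX class.

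**Step 2: let a share f of the 855 have an 11-14 week result.** The protocol gives no value for f, so each value below is an assumption. Prevalence, sensitivity and specificity are held fixed, which means that loss is taken as unrelated to ADNEX result and outcome. The sensitivity column is the exact half-width at 73% on 0.08 × n malignancies.

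| Assumed f | n | ADNEX-positives | FDR half-width | Sensitivity half-width |
|---|---|---|---|---|
| 100% | 855 | 83.0 | 10.97% | 11.06% |
| 95% | 812 | 78.8 | 11.3% | 11.4% |
| 90% | 770 | 74.7 | 11.6% | 11.7% |
| 80% | 684 | 66.4 | 12.3% | 12.4% |
| 70% | 598 | 58.1 | 13.2% | 13.3% |
| 50% | 428 | 41.5 | 15.6% | 15.8% |

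**Step 3: break-even.** The FDR half-width is 11.49% at n = 780 and 11.50% at n = 779. The rounded 11% therefore needs about 780 women, and 780 / 855 = 91%. Sensitivity passes 11.5% slightly sooner, at about n = 793 (793 / 855 = 93%).

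**Step 4: how the kind of loss matters.** With the FDR held at 39.8%, the half-width is 11.47% with 76 positives and 11.55% with 75. Losing about 8 of the 83 positives is thus enough to turn 11% into 12%. If only ADNEX-negative women are lost, for example early masses that resolve, the 83 positives remain and the FDR half-width stays at 10.97%.

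**Step 5: the plan's own rows.** The first precision table already prints 12% for both FDR and sensitivity at n = 765 to 675, and 13% for both at n = 630 to 585.

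**The case against.** The strongest reply is that nothing has been miscalculated and no loss has been shown. The table is right for the n it uses. The protocol gives no late-presentation share. The design favours a high one, because early masses are re-scanned at 11-14 weeks and the Background links rising detection to routine first-trimester ultrasound. Up to about 9% of recruits could lack the result before the rounded figure moves, and a 5% loss changes nothing at that rounding. This is an estimation study with no minimum precision that 12% or 13% would fail. A reader can look up a smaller n in the table, and both the target and the three-year duration are loosely worded.

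All of this stands as to size. It does not remove the mismatch. The protocol makes an explicit numerical claim for its primary outcome and attaches it to a count that elsewhere means all recruits. Nothing in the protocol shows that the loss stays within the 9% margin. Since the claim is on the page, it is not a detail left to an analysis plan.

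A reader might infer three stronger things that the documents do not support:

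- **That the 11% is an arithmetic error.** It is not; it reproduces exactly for 855 evaluable women.
- **That the study is too small, or will lose a particular share.** The shares above are assumptions, and loss confined to resolved, ADNEX-negative masses would hardly matter for the FDR.
- **That the other performance figures can simply be read as any-gestation results.** Sections 7.2 and 8.1 also plan C-index, calibration and clinical utility at 11-14 weeks, so the same question of which n applies arises there.

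**Conclusion.** The concern holds as a mismatch of denominator. The protocol's 11% for the primary FDR is correct for 855 women with an 11-14 week ADNEX result, but 855 is its any-gestation recruitment total, and it foresees recruits without that result. The figure survives rounding only if at least about 91% of recruits contribute; a share of 70% to 90% would make it 12% to 13%. These sizes assume the 8% prevalence, the 73% and 95.8% accuracy, exact intervals, and loss unrelated to ADNEX result and outcome. The true share cannot be obtained from the protocol. The consequence is moderate: the validity of the design is untouched, but the stated precision of the primary estimate is not secured by the recruitment rules.

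**What to change.** 1. Keep 855 as the recruitment total. In section 8, state the assumed share of recruits who will have an 11-14 week ADNEX result.
2. Quote the primary FDR precision, and the sensitivity precision for 11-14 weeks, for that number from the first precision table: 12% for n = 765 to 675, or 13% for n = 630 to 585.
3. Alternatively, if 855 is meant to be women scanned at 11-14 weeks, say so and reconcile it with section 6.1 (recruitment at any gestation) and section 6.5 (855 as the recruitment target).
4. State which n the C-statistic and observed-to-expected statements refer to, and do not quote the 855-based figures for the 11-14 week analysis without the same adjustment. The net-benefit requirements are less exposed, since the largest is 325 women.

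The cost is some rewording of section 8 and probably a slightly less favourable stated precision. Options 1 and 2 need no extra patients and no change in conduct.
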